4. SUBJECT POPULATION

4.1. Number of Subjects and Subject Selection

This study will target approximately 20 subjects for enrollment who are equal to or greater than 18 years of age with PSC and compensated cirrhosis.

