6.4. Treatment Assessments

6.4.1. Week 1, Week 4, Week 8, and Week 12 (\pm 3 days)

Subjects should be instructed to fast (no food or drink, except water), starting from midnight (00:00) or earlier, as appropriate, on the evening prior to ensure an approximate 8-hour fast prior to the fasted blood sample collection the next morning.

Subjects should also be instructed to HOLD their dose of study drug on the day of their visit until all blood sample collections have been completed.

The following treatment procedures/assessments are to be completed and documented at these in-clinic visits:

- For subjects with history of IBD (as appropriate, see Section 6.8.6):

IBD symptom severity assessment (Week 4, Week 8, and Week 12)

any evidence of active IBD seen on routinely performed colonoscopy will be captured at all in-clinic visits

- Symptom-driven physical examination including ascites and HE assessments
- Record vital signs and body weight
- Obtain blood samples for:

Chemistry

eGFR

Hematology

Coagulation Panel

Lipid Profile (Week 4, Week 8, and Week 12)

C-peptide, Insulin and HbA_{1c} (Week 12)

Biomarkers (Week 1, Week 4, Week 8, and Week 12)

cc1 [REDACTED]
[REDACTED]
[REDACTED]
[REDACTED]

The date and time of the previous study drug dose will need to be documented

cc1 [REDACTED]

- CP and MELD scores
- Obtain urine samples for:

Urine pregnancy testing for females of childbearing potential only at Week 4, 8, and 12

- Collect stool sample (Week 12) for bile acids by mass spectrometry (if available)
- Perform FibroScan at Week 12
- Record all CMs that the subject has taken since the previous visit
- Record any SAEs and all AEs occurring since the previous visit
- Dispense the study drug as directed by IWRS (Week 4 and Week 8)
- Review study drug compliance and study drug administration instructions with subject

Reconcile study drug administration using pill counts

In the case of a PI approved study drug dose interruption, subjects will have weekly telephone follow-up assessments as detailed in Section 6.4.2. During the study drug dose interruption, subjects are otherwise not required to complete in-clinic assessments unless deemed necessary given the rationale for their study drug dose interruption (eg, Close Observation for drug-induced liver injury [DILI], follow up of non-DILI laboratory abnormalities).

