1. INTRODUCTION

This statistical analysis plan (SAP) describes the statistical analysis methods and data presentations to be used in tables, figures, and listings (TFLs) in the clinical study report (CSR) for Study GS-US-428-5443. This SAP is based on the study protocol amendment 3 dated 15 January 2021 and the electronic case report form (eCRF). The SAP will be finalized before database finalization. Any changes made after the finalization of the SAP will be documented in the CSR.

The study enrollment was terminated early by the sponsor on 30 July 2021 due to recruitment challenges in a rare disease population.

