3.5. Missing Data and Outliers

3.5.1. Missing Data

In general, missing data will not be imputed unless methods for handling missing data are specified. Exceptions are presented in this document.

For missing last dosing date of study drug, imputation rules are described in Section 4.2. The handling of missing or incomplete dates for AE onset is described in Section 7.1.5.2.

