3.7.2. Analysis Visit Windows

Subject visits might not occur on protocol-specified days. Therefore, for the purpose of analysis, observations will be assigned to analysis windows.

On-treatment visit windows will be calculated from study Day 1 or the first post-interruption study drug dosing date for selected efficacy measures, elastography, and safety laboratory data.

Selected safety and efficacy data, unless otherwise specified, collected up to and including the last dosing date + 30 days, will be mapped according to the following analysis windows unless the nominal visit name is early termination (ET) or Follow-Up.

The analysis windows for selected measures are provided in [Table 3-1](#) to [Table 3-3](#). The algorithm for assigning baseline analysis window does not apply to the liver tests (ALP, total bilirubin, ALT, AST, and GGT). For these 5 parameters, the baseline values will be determined by averaging the values obtained at Screening and Baseline/Day 1, and no specific study day is associated with the average values.

Table 3-1. Analysis Visit Windows for Chemistry, eGFR, Hematology, Coagulation, Child-Pugh (CP)/ Model for End-stage Liver Disease (MELD) Scores, Pruritus VAS, 5D-Itch and Biomarkers, Including hsCRP, ELF™ Score and Components, FibroSURE/FibroTest® and Selected Components, Bile Acids, FGF19, C4.

Nominal Visit	Nominal Study Day/Post-interruption Study Day	Visit Window Study Day/Post-interruption Study Day	
		Lower Limit	Upper Limit
Baseline/Post-interruption Day 1	1	(none)	1
Week 1/Post-interruption Week 1	8	2	18
Week 4/Post-interruption Week 4	29	19	42
Week 8/Post-interruption Week 8	57	43	70
Week 12/Post-interruption Week 12	85	71	≥85

Table 3-2. Analysis Visit Windows for IBD Symptoms

Nominal Visit	Nominal Study Day/Post-interruption Study Day	Visit Window Study Day/Post-interruption Study Day	
		Lower Limit	Upper Limit
Baseline/Post-interruption Day 1	1	(none)	1
Week 4/Post-interruption Week 4	29	2	42
Week 8/Post-interruption Week 8	57	43	70
Week 12/Post-interruption Week 12	85	71	≥85

Table 3-3. Analysis Visit Windows for QoL Questionnaires and FibroScan

Nominal Visit	Nominal Study Day/Post-interruption Study Day	Visit Window Study Day/Post-interruption Study Day	
		Lower Limit	Upper Limit
Baseline/Post-interruption Day 1	1	(none)	1
Week 12/Post-interruption Week 12	85	2	≥ 85

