 - If there is more than 1 record on the selected day, the average will be taken for continuous data and the worst severity will be taken for categorical data, unless otherwise specified.
 - FGF19 and C4 obtained on the same day will not be averaged. The predose value would be selected to represent the study visit, when the data are summarized by study visit and not by timepoint within a visit. The summary by timepoint is described separately in Section 9.3.

Liver stiffness by transient elastography data in each analysis visit window will be chosen based on the following rules:

- For baseline, measurements by M probe will be selected for analysis if available, otherwise measurements by XL probe will be selected.
- For postbaseline visits, measurements by the same probe type (XL or M) selected for the subject at baseline will be selected in each analysis visit window. If no measurement by the same probe type as baseline is available, the analysis value for the corresponding postbaseline visit will be considered missing. If there are multiple postbaseline records by the same probe type as baseline, the rules to choose postbaseline continuous measurements as described above will apply.

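### The FibroScan rule fixes the probe from baseline alone, so a subject with M and XL readings at baseline and only XL at Week 12 is set to missing although a matched XL pair exists

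*SAP*

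**What the plan says.** SAP 3.7.3 ends with separate rules for liver stiffness by transient elastography. They work in sequence.

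- Baseline: "For baseline, measurements by M probe will be selected for analysis if available, otherwise measurements by XL probe will be selected".
- After baseline: "measurements by the same probe type (XL or M) selected for the subject at baseline will be selected in each analysis visit window".
- If that type is absent: "If no measurement by the same probe type as baseline is available, the analysis value for the corresponding postbaseline visit will be considered missing".

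On missing values, SAP 3.5.1 states: "In general, missing data will not be imputed unless methods for handling missing data are specified". The visible text makes no exception for FibroScan.

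The protocol schedules FibroScan at Screening (6.2.1), at Week 12 (6.4.1, "Perform FibroScan at Week 12") and at early termination (6.4.3). SAP Table 3-3, "Analysis Visit Windows for QoL Questionnaires and FibroScan", has two windows: baseline, up to Day 1 with no lower limit, and Week 12, from Day 2 onward. Early-termination data are summarized as a separate visit (SAP 3.7.2).

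**The concern.** Requiring the same probe within a subject is sound, because a change computed across two probe types would mix a device difference with a change in stiffness. The weakness is the order of the steps. The probe is settled before anyone checks which type is available later, and nothing allows a return to the other type. When both types are on file at baseline and only XL at Week 12, the rule finds no match, although a same-probe comparison is possible with data already collected.

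The SAP's own text allows for two probe types at baseline, since an M-first preference has an effect only when both are on file. The open lower limit of the baseline window means that the two readings could come from one pre-dose visit or from two.

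At stake is one Week 12 stiffness value, and the corresponding change from baseline, for each such subject.

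**Working it through.** The plan gives no figure to reproduce: it has no power calculation and no rate of dual-probe use. The check is an enumeration of the rule.

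**Inputs.** Probe selection and the missing-value rule come from SAP 3.7.3, the absence of imputation from SAP 3.5.1, and the FibroScan windows from SAP Table 3-3. The planned size comes from Protocol 4.1 ("This study will target approximately 20 subjects for enrollment"), and the early stop from SAP 1 ("The study enrollment was terminated early by the sponsor on 30 July 2021"). The final number of subjects is not stated.

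**Step 1: apply the SAP rule.** At each of the two visits the readings on file can be none, M only, XL only or both, which gives 4 × 4 = 16 combinations. The entries show the probe used for the Week 12 value.

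| Baseline | Week 12: none | Week 12: M | Week 12: XL | Week 12: both |
|---|---|---|---|---|
| none | missing | missing | missing | missing |
| M | missing | M | missing | M |
| XL | missing | missing | XL | XL |
| both | missing | M | **missing** | M |

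**Step 2: apply a joint rule.** Take the probe types present at both visits; use M if it is among them, otherwise XL; set the visit to missing if there are none. Fifteen entries are unchanged. The bold entry becomes XL. The combinations M only then XL only, and XL only then M only, stay missing under both rules, because no matched pair exists.

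**Step 3: size per affected subject.** One subject is 1/20 = 5% of the pairs if all of about 20 planned subjects contribute a pair. With an assumed 10 pairs it is 1/10 = 10%. These are shares per affected subject, not expected losses.

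**Step 4: expected loss under assumed frequencies.** The expected number of lost pairs is n × q, where q is the share of subjects with the pattern. The documents give no q, so all values here are assumptions.

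| Assumed q | n = 20 | n = 10 (assumed) |
|---|---|---|
| 0% | 0 | 0 |
| 1% | 0.2 | 0.1 |
| 5% | 1 | 0.5 |
| 10% | 2 | 1 |

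**The case against.** The best defence is that the rule is a deliberate convention. It gives each subject one baseline, fixed without reference to later data, and the case it handles badly may never arise. Choosing the probe jointly makes the baseline depend on which later records exist, and could give one subject different baselines for different visits. That cost is real, though small with a single scheduled on-treatment scan. The remark on frequency also stands.

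A looser reading of the rule does not remove the problem. If the unselected XL reading counted as a baseline type, the Week 12 XL value would be kept but compared with an M baseline, which is what the rule is meant to prevent. The reference to the type selected at baseline excludes that reading in any case.

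A reader might infer three stronger points, and the documents support none of them.

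- *The pattern arises because operators move to XL when M is unsatisfactory.* The protocol asks only that FibroScan be performed and says nothing about probe order or switching. The selection rules in SAP 3.7.3 are introduced as applying to valid, nonmissing records. If M failed at baseline and that carries over to the elastography rules, XL would be selected and would pair normally with XL at Week 12.
- *The loss is selective against subjects who need XL.* Subjects with XL only at both visits keep their pair, as do those with XL only at baseline and both types at Week 12.
- *The loss cannot be recovered.* The Week 12 window opens on Day 2, and SAP 3.7.2 allows unscheduled data to be assigned to windows. An unscheduled on-treatment M scan could therefore supply a value, although none is planned.

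The SAP's efficacy section is redacted, so the presentation of FibroScan change cannot be seen. The only visible FibroScan summary is the baseline characteristic in SAP 5.2.

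**Conclusion.** The point holds as a narrow gap in the rule. SAP 3.7.3, read literally, discards an existing XL pair in one of 16 availability combinations, and no visible text provides a fallback. It rests on two assumptions: that valid readings with both probes can be on file at baseline, which the M-first preference itself implies, and that the redacted sections contain no exception.

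The number of subjects affected cannot be derived and may be zero. Each would remove one pair of at most about 20. The primary endpoint is safety and tolerability, judged by adverse events, laboratory tests and vital signs (Protocol 8.1.2), and no formal testing is planned (SAP 3.4), so no main conclusion depends on this. It is an optional improvement and not evidence of bias in the FibroScan results.

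**What to change.** For change from baseline in liver stiffness, replace the sequential choice in SAP 3.7.3 with a joint one:

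- use the probe type with valid readings at both baseline and the postbaseline visit;
- use M if both types qualify;
- set the visit to missing only when no type is present at both.

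Keep the M-then-XL order for the baseline-characteristics table in SAP 5.2, and footnote any subject whose baseline for change differs from the one shown there.

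The cost is about one sentence of SAP text and a few lines of programming, plus the footnoted mismatch for any affected subject. The same-probe requirement is kept and the other 15 combinations are unaffected. If the SAP is already final, SAP 1 provides the route: document the change in the clinical study report.

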4. SUBJECT DISPOSITION

4.1. Subject Enrollment and Disposition

Key study dates (ie, first subject screened, first subject enrolled, last subject enrolled, last subject last visit for the primary endpoint, and last subject last visit for the clinical study report) will be provided.

A summary of subject disposition will be provided. This summary will present the number of subjects screened, the number of subjects enrolled, and the number and percentage of subjects in each of the categories listed below. For the Safety Analysis Set category, the denominator for the percentage calculation will be the total number of subjects enrolled for each column. For all other categories, the denominator for the percentage calculation will be the total number of subjects in the Safety Analysis Set for each column.

- Safety Analysis Set
- PK Analysis Set for each analyte
- [REDACTED]
- PD Analysis Set for each parameter
- [REDACTED]
- Had PI approved study drug interruption and study drug dose level when the interruption occurred
- Completed study drug
- Did not complete study drug with reasons for premature discontinuation of study drug
- Completed study
- Did not complete the study with reasons for premature discontinuation of study

In addition, the total number of subjects who were enrolled, and the number of subjects in each of the disposition categories listed above will be displayed in a flowchart.

The following by-subject listing will be provided by subject ID number in ascending order to support the above summary tables:

- Reasons for premature study drug or study discontinuation

4.2. Extent of Study Drug Exposure and Adherence

Extent of exposure to study drug will be examined by assessing the total duration of exposure to study drug.

4.2.1. Duration of Exposure to Study Drug

Total duration of exposure to study drug will be defined as last dosing date minus first dosing date plus 1 (minus study drug interruption duration if there is a PI-approved study drug interruption, where the study drug interruption duration is defined as first post-interruption dosing date minus last dosing date prior to drug interruption minus 1), regardless of any temporary interruptions in study drug administration, and will be expressed in weeks using up to 1 decimal place (eg, 4.5 weeks). If the last study drug dosing date is missing, the latest date among the study drug end date, clinical visit date, laboratory sample collection date, and vital signs assessment date that occurred during the on-treatment period will be used for subjects included in the final analyses.

The total duration of exposure to study drug will be summarized using descriptive statistics and using the number (ie, cumulative counts) and percentage of subjects exposed through the following time periods: 1 day, 1 week, 4 weeks, and every 4 weeks thereafter. Summaries will be provided for the Safety Analysis Set.

4.2.2. Adherence to Study Drug

The total number of doses administered will be summarized using descriptive statistics.

The presumed total number of doses administered to a subject will be determined by the data collected on the drug accountability eCRF using the following formula:

Total Number of Doses Administered =

$$\left(\sum \text{No. of Doses Dispensed} \right) - \left(\sum \text{No. of Doses Returned} \right)$$

4.2.2.1. Prescribed Adherence

The level of prescribed adherence to the study drug regimen will be determined by the total amount of study drug administered relative to the total amount of study drug specified by the protocol for a subject who completes treatment in the study, ie, 112 tablets. For subjects who require a study drug interruption, the adherence calculation will account for the initial drug amount and the subsequent drug amount (after the interruption) at the respective dose level. For example, if a subject takes ten 100 mg tablets and requires an interruption, and subsequently takes twelve 100 mg tablets post interruption before discontinuing, the denominator would be 122 (28 + 28 * 2 + 10 + 28, the last term 28 is because the protocol specifies that subjects should complete 28 consecutive days at each dose level).

The level of prescribed adherence will be expressed as a percentage using the following formula:

$$\text{Prescribed Adherence (\%)} = \left(\frac{\text{Total Amount of Study Drug Administered}}{\text{Total Amount of Study Drug Specified by Protocol}} \right) \times 100$$

Descriptive statistics for the level of prescribed adherence with the number and percentage of subjects belonging to adherence categories (eg, < 75%, \geq 75 to < 90%, \geq 90%) will be provided by total for the Safety Analysis Set.

A by-subject listing of study drug administration and drug accountability will be provided separately by subject ID number (in ascending order) and visit (in chronological order).

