3.2. Study Treatments

Individual subjects will receive escalating doses of CILO 30 mg (1 × 30 mg tablet), 60 mg (2 × 30 mg tablets), then 100 mg (1 × 100 mg tablet), administered orally once daily. If tolerated, subjects will dose escalate after 4 weeks on each dose.

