5.3. Dosage and Administration of CILO

CILO tablets will be provided by Gilead Sciences, Inc. During the treatment phase of the study, each subject will be supplied with open-label bottles of CILO tablets.

Enrolled subjects will start with 1 bottle containing 30 CILO tablets and will be instructed to take one (30 mg tablet) orally once daily for 4 weeks. Upon dose escalating, subjects will be provided with 2 bottles of CILO, each containing 30 tablets, and will be instructed to take two (30 mg) tablets orally once daily for 4 weeks. Upon final dose escalation, subjects will be provided with 1 bottle of CILO containing thirty 100 mg tablets and will be instructed to take one (100 mg) tablet orally once daily for 4 weeks.

The study drug should be taken at approximately the same time each day. A dose will be considered missed if the subject cannot take the dose within 12 hours of their regular dosing time. If a subject misses a dose, the subject should take their next dose at the regular dosing time.

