5.6. Accountability for CILO

The investigator is responsible for ensuring adequate accountability of all used and unused study drug. This includes acknowledgment of receipt of each shipment of study drug (quantity and condition). All used and unused study drug dispensed to subjects must be returned to the site.

Study drug accountability records will be provided to each study site to:

- Record the date received and quantity of study drug kits
- Record the date, subject number and the study drug kit number dispensed
- Record the date, quantity of used and unused study drug returned, along with the initials of the person recording the information

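### Does setting adherence against 112 tablets, when the preceding section counts doses, distort the adherence summary?

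*SAP*

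**What the plan says.** SAP 4.2.2 sets out a count of doses, dispensed minus returned: "The presumed total number of doses administered to a subject will be determined by the data collected on the drug accountability eCRF". SAP 4.2.2.1 then defines prescribed adherence as the amount of drug taken divided by the amount the protocol specifies. For a completer that is the "total amount of study drug specified by the protocol for a subject who completes treatment in the study, ie, 112 tablets". In its worked example a subject takes ten 100 mg tablets, interrupts, takes twelve more and stops; there "the denominator would be 122". Descriptive statistics and category counts "will be provided by total for the Safety Analysis Set". The categories, offered as examples, are below 75%, 75% to below 90%, and 90% or more. The same section also calls for a by-subject listing of drug administration and accountability, ordered by visit.

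In Protocol 3.2 the first stage is one 30 mg tablet a day, followed by "60 mg (2 × 30 mg tablets), then 100 mg (1 × 100 mg tablet), administered orally once daily". Protocol 5.3 confirms that subjects in the middle stage "will be instructed to take two (30 mg) tablets orally once daily for 4 weeks".

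**The concern.** Two adjacent sections use different nouns for the same accountability data, and at 60 mg the nouns are not interchangeable. Read literally, the only administered quantity with a formula is a number of doses, yet the denominator is in tablets. A programmer who joined the two would report 75% for perfect intake.

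Settling on tablets leaves a second worry. The 60 mg stage counts double because of tablet strength, so the same number of missed days can fall in different categories depending on the stage. With results pooled over stages, a subject who took none of the 100 mg stage would still score exactly 75.0% and stay out of the lowest category. In a dose-escalation study of tolerability, one would want to see where dosing failed.

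**Working it through.** **Inputs.** Tablets per day: 1, 2 and 1 (Protocol 3.2 and 5.3). Stage length: 28 days, three stages, 84 dosing days (Protocol 3.1). Cut-points: 75% and 90% (SAP 4.2.2.1).

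**1. The plan's own figures.** Completer: 28 × 1 + 28 × 2 + 28 × 1 = 112. Worked example: 28 + 56 + 10 + 28 = 122. Both reproduce exactly, as tablet counts.

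**2. Stage weights (30, 60, 100 mg).**
- Tablets: 28, 56, 28 of 112 = 25%, 50%, 25%.
- Dosing days: 28 of 84 = 33.3% each.
- Milligrams: 840, 1680, 2800 of 5320 = 15.8%, 31.6%, 52.6%.

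**3. Effect of d missed days.** Tablets, missed at 60 mg: (112 − 2d)/112. Tablets, missed at 30 or 100 mg: (112 − d)/112. Doses, any stage: (84 − d)/84.

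| d | Tablets, 60 mg | Tablets, 30 or 100 mg | Doses |
|---|---|---|---|
| 5 | 91.1% | 95.5% | 94.0% |
| 6 | 89.3% | 94.6% | 92.9% |
| 7 | 87.5% | 93.8% | 91.7% |
| 11 | 80.4% | 90.2% | 86.9% |
| 12 | 78.6% | 89.3% | 85.7% |
| 28 | 50.0% | 75.0% | 66.7% |

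For 6 to 11 missed days the tablet-based category depends on the stage, around the 90% cut. For 15 to 28 missed days it does so around the 75% cut: at 60 mg from 82/112 = 73.2% down to 50.0%, and at 30 or 100 mg from 97/112 = 86.6% down to 75.0%.

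**4. Doses over tablets.** Full intake: 84/112 = 75.0%. One missed dose: 83/112 = 74.1%. Worked example: (28 + 28 + 10 + 12)/122 = 78/122 = 63.9%.

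**5. Worked example in one unit.** Tablets: (28 + 56 + 10 + 12)/122 = 106/122 = 86.9%. Doses: 78/(28 + 28 + 10 + 28) = 78/94 = 83.0%. Both lie in the middle category. The 100 mg stage alone is (10 + 12)/(10 + 28) = 22/38 = 57.9%.

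**6. Which unit the SAP intends.** SAP 4.2.2.1 does not name the 4.2.2 dose count as its numerator; it speaks of an amount of drug. Its example states intake in tablets and doubles the 60 mg term. Drug is supplied in bottles of 30 tablets (Protocol 5.2.2), and sites reconcile intake by pill count (Protocol 6.4.1 and 6.4.3). To reach the figures in step 4, a programmer would have to halve the 60 mg pill count and then divide by a number labelled tablets.

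**7. Where the stage can be seen.** Drug is dispensed at Day 1, Week 4 and Week 8 (Protocol Appendix 2), which are the stage boundaries for subjects who escalate on schedule. Protocol 5.6 lists among the site's accountability entries "Record the date, subject number and the study drug kit number dispensed". A listing by visit therefore separates the stages. SAP 4.1 also reports the dose level at which an approved interruption occurred, and SAP 4.2.1 gives cumulative exposure in 4-week steps.

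**The case for a change.** The best case for a change sets the unit wording aside. Even with tablets on both sides, the 50% weight follows neither days (33.3%) nor milligrams (31.6%); it arises only because 60 mg is given as two tablets. A figure in once-daily doses would mean the same in every stage, and rows by stage would show the 57.9% that the example's 86.9% hides. If no more than the planned 20 or so subjects were enrolled, one reclassified subject moves a category by at least 1/20 = 5 percentage points. The edit is a few sentences.

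The arithmetic stands, and so does the point that the dose total in SAP 4.2.2 is ambiguous: 84 or 112 for full intake. The need for a different metric does not follow. The SAP defines adherence by amount of drug and nowhere promises equal weight per day. A tablet count registers, without any extra rule, a subject who takes one of two tablets throughout the 60 mg stage: (112 − 28)/112 = 75.0%. A dose count needs a half-dose convention, and stage rows need returned 30 mg tablets assigned to the 30 mg or the 60 mg stage. An overall 84-dose figure still could not show which stage was missed. The category crossings also rest on cut-points that the SAP gives only as examples.

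**Conclusion.** No change is needed. The word for doses in SAP 4.2.2 is loose, but the worked example, the denominator label and pill-count reconciliation all point to tablets, and an analyst would label the table so. On that reading, tablet and dose scores for a fixed number of missed days differ by at most 66.7 − 50.0 = 16.7 percentage points (the whole 60 mg stage missed), and by 91.7 − 87.5 = 4.2 points for seven days missed at 60 mg. That is a choice between two defensible measures.

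Nothing rests on the choice. The summary is descriptive, SAP 3.4 plans no formal testing, and no endpoint or analysis set uses adherence. SAP 1 and 2.3 record that enrolment ended early and that outputs were cut back for limited numbers. In so small a study the by-subject listing shows the pattern more directly than extra summary rows would.

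This assumes that the accountability eCRF records tablets and that the listing shows tablets dispensed and returned by visit. The documents do not show the form. If it recorded once-daily doses instead, the analyst would have to convert the 60 mg stage before using 112.
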